## 7 Statistical Plan

The project coordinator and [name] will be the primary database managers. [name] will oversee the processing of the neuroimaging data. [name] will oversee the completion of Aims 1-2 and [name] will oversee Specific Aim 3.

## 7.1 Sample Size Rationale

This is a pilot study to obtain pilot data for larger studies. One goal of any pilot study is to obtain variance estimates so sample sizes for a larger study can be determined. Because this is a pilot study, we do not focus on significance ( $p < .05$ ). Nonetheless, our own research supports a large effect of ovarian hormones on binge eating (our primary Aim): in linear models, E2 and P4 accounted for  $R^2 = 24\%$  of the variance in binge eating and within-subject correlations between E2 and binge eating indicate a maximum Cohen's  $d = 1.4$  and between P4 and binge eating a maximum Cohen's  $d = 1.7$ . Calculating power based on the effect of P4 on binge eating ( $d = 1.7$ ; given that the effect of OC administration on binge eating is hypothesized to occur via the absence of P4),  $n = 15$ , and  $\alpha = .05$ , we have  $> 95\%$  to detect an effect.

Further, a general power calculation (estimating the required effect size to determine a significant effect with a projected sample size), with a projected sample of  $n = 15$ , an effect size of .77 is required to detect a treatment difference at a two-sided .05 significance level at 80% power (calculated in G\*Power based off of projected sample size and desired power).

Finally, we take steps to reduce missing data by having the study coordinator review all in-person assessment measures for completeness and skipped items.

## 7.2 Statistical Methods

Statistical analyses are completed using the most recent version of SAS. Primary outcome measures are self-reported binge eating and brain activation in response to reward examined via fMRI (see below). All assessment measures are empirically valid. Measures will be scored according to standard conventions and scoring procedures and are primarily continuous. Descriptive statistics and graphics will be used to screen for errors, outliers, and potential influential observations and to check distributional assumptions.

### **PRIMARY OUTCOMES**

**Binge eating** will be defined as: 1) the EPSI subscale binge eating score (T1, T2), which represents a continuous score of symptoms over the previous month (higher scores indicate more symptoms); 2) weekly binge eating frequency based on the weekly assessment (higher scores indicate greater frequency). **Reward response** will primarily be defined by brain activation (BOLD signal) in response to the MIDT as measured by fMRI. Specifically, brain activation in dopamine-reward pathways, ROI include: nucleus accumbens, dorsal striatum, and DLPFC.

### **SECONDARY OUTCOMES**

Self-report questionnaires of reward responsivity. The **BIS/BAS**, **SPSRQ**, and **Kirby Delay Discounting** will be included as self-report measures of reward response. Specifically, we will include the behavioral inhibition subscale of the BIS/BAS as self-report correlate of the reward response. The SPSRQ will be used to assess sensitivity to reward sensitivity. Kirby Delay Discounting will be defined by the individual's rate of delay discounting ( $k$ ).

*Hypotheses.* Our overarching hypothesis for the following aims is that post-ovulation changes in ovarian hormones are responsible for the changes in binge eating observed across the menstrual cycle and that the mechanism underlying this change in change in brain activation in response to reward. Thus, we hypothesize

that OC will be beneficial for the primary outcomes of interest. We hypothesize “benefical” may manifest in one of two ways: *hypothesis 1a*: symptomatology *decreases* from OC use or *hypothesis 1b*: variability of symptoms that occurs during a natural menstrual cycle does not occur with OC use.

As such, our null hypothesis is that there is no effect of OC on behaviors of interest.

**Aim 1: Investigate the effect of ovarian hormone stabilization on eating behaviors in women with binge eating.**

Null hypothesis: There is no effect of birth control on binge eating.

Alternative hypothesis: Birth control administration directly changes binge eating behaviors.

Dependent variable: binge eating (EPSI subscale, weekly binge eating frequency)

Independent variable: treatment condition (T1 vs T2)

**Analysis**

A paired sample t-test will compare within-person change between pre- and post-intervention outcomes (EPSI subscale score; weekly frequency). Binge eating variability/fluctuation pre- and post- intervention is tertiary explored by plotting weekly variance estimates in reported binge eating frequency.

**Aim 2: Examine the effect of ovarian hormone stabilization on brain activation in reward pathways in women with binge eating.**

Null hypothesis: Birth control has no effect in reward pathways in women with binge eating as measured by fMRI.

Alternative hypothesis: Birth control administration has a measurable difference on brain activation in reward pathways in women with binge eating as measured by fMRI.

Dependent variable: ROI: nucleus accumbens, dorsal striatum, and DLPFC.

Independent variable: treatment condition (T1 vs T2).

Dependent variable (percent signal changed in ROI): Nucleus accumbens, dorsal striatum, and DLPFC connectivity will be assessed during the MIDT fMRI task at study visits T1 and T2.

Functional connectivity expresses the statistical dependency among activations in different brain regions and results in undirected (symmetrical) connectivity matrices and will be calculated according to standard procedures (Walsh et al., 2017). We will use a generalized psychophysiological interaction (gPPI) approach for detecting context-dependent functional connectivity (Cisler, Bush, & Steele, 2014; McLaren, Ries, Xu, & Johnson, 2012). Replicating the methods of Walsh et al. (2017), we will use an ROI approach to target the nucleus accumbens, dorsal striatum, and DLPFC, which will be defined using the Harvard-Oxford subcortical atlas. Voxel-wise models will be used to evaluate connectivity. For each participant, mean fMRI time courses will be extracted using the “fslmeans” program in FSL, then multiplied by each psychological regressor of interest (i.e., task condition) to form the PPI interaction terms. The gPPI model will include physiological and psychological regressors, as well as their interaction terms to describe the unique effect of these interactions above and beyond the main effects of seed time courses and task conditions. Our primary contrast of interest will evaluate the difference between connectivity during presentation of reward versus non-rewarding stimuli. Contrasts of interest will include win vs. non-win outcomes. This allows for the characterization of connectivity patterns specific to reward response.

Analysis: Treatment phase differences will be evaluated with respect to seed-based connectivity specific to reward processing using a paired t test.

Secondary outcomes will be analyzed as described in Aim 1: paired t test will compare within-person change between pre- and post-intervention. Reward responsibility (BIS/BAS, SPSRQ, Kirby Delay Discounting) will be the dependent variable and treatment condition the independent variable.

We will also tertiary explore Pearson correlations between activation signals and change in brain activation and change in binge eating between T1 and T2. Binge eating will be defined by the EPSI subscale score. Reward response will include brain activation in ROI.

*Missingness.* We will use multiple imputation to correct for data determined to be missing at random, given that it is a reliable method for obtaining valid inferences in both behavioral and fMRI research (Rubin, 1987; Vaden, Gebregziabher, Kuchinsky, & Eckert, 2012). Data for any dropouts will be compared with data for those who complete the study to determine the extent to which excluding their data will introduce selection bias, and selection bias will be identified as a weakness in any resulting publications or presentations. Finally, as described above, we take steps to reduce missing data by having the study coordinator review all in-person assessment measures for completeness and skipped items. If missing data is considerable, which we consider unlikely for the data collected in person at study visits, longitudinal analysis via linear mixed-effects models will be implemented.

*Sensitivity Analysis.* In addition to the statistical tests described above, we will tertiary use sensitivity analyses to evaluate the robustness of the main results of the study to reasonable perturbations of the statistical methods and assumptions used and to help ensure reproducibility of the main results. Sensitivity analysis will address the inclusion/exclusion of questionable data values (i.e., outliers), the use of alternative methods of coping with missing values and dropouts, and modeling assumptions. We will additionally examine whether associations differ based on specific ED diagnosis or frequency of binge eating behaviors at baseline.

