### 3.2 Outcome Variables

The primary endpoints for the Specific Aims are: 1) self-reported binge eating; 2) brain activation in dopamine-reward pathways, ROI include: nucleus accumbens, dorsal striatum, and DLPFC. Secondary end points include self-report measures of reward.

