**Table 2: Study Visit Procedures**

Primary Study Procedures					
Procedure	T0	T1	T2	T3	Monthly Visit
Informed Consent	x				
Clinical Health Interview	x				
Venipuncture	x				x
Side Effects and Adherence			x		x
Self-report Questionnaires					
Demographics	x				
EPSI	x	x	x	x	x
BIS/BAS		x	x	x	
SPSRQ		x	x	x	
Kirby Delay Discounting Questionnaire		x	x	x	
fMRI Tasks					
MIDT		x	x		

Participants. Women between the ages of 18-34 with a normal weight binge-eating syndrome. All participants will undergo the same drug protocol in an open label manner.

OC Administration. Participants will begin taking OC for 84 days (i.e., 12-weeks) continuously on the first day of their period after T1. During the final two weeks of OC administration, T1 assessments will be repeated (T2).

Clinical Assessments. Specific study procedures, measures used to obtain primary and secondary outcomes, and the assessment schedule for the protocol are shown in **Table 2**. All study measures are empirically valid and reliable. The focus of this pilot study is on the primary outcomes of binge eating and brain activation in response to reward examined via fMRI.

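### The primary imaging endpoint is activation in three regions, but the only T1–T2 imaging test named is on connectivity

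*Combined protocol and SAP*

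**What the plan says.** Four places set the imaging endpoint as activation.

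- Section 3.2 lists as a primary endpoint "brain activation in dopamine-reward pathways, ROI include: nucleus accumbens, dorsal striatum, and DLPFC".
- Section 6 (Clinical Assessments, under Table 2) says "The focus of this pilot study is on the primary outcomes of binge eating and brain activation in response to reward examined via fMRI".
- Section 7.2 opens with "Primary outcome measures are self-reported binge eating and brain activation in response to reward examined via fMRI".
- The Primary Outcomes text in 7.2 says that reward response "will primarily be defined by brain activation (BOLD signal) in response to the MIDT as measured by fMRI".

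The Aim 2 alternative hypothesis agrees: "Birth control administration has a measurable difference on brain activation in reward pathways in women with binge eating as measured by fMRI".

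The Aim 2 methods then turn to connectivity. The dependent-variable line reads "Dependent variable (percent signal changed in ROI): Nucleus accumbens, dorsal striatum, and DLPFC connectivity will be assessed during the MIDT fMRI task". A generalized psychophysiological interaction (gPPI) model follows, and the Analysis line is "Treatment phase differences will be evaluated with respect to seed-based connectivity specific to reward processing using a paired t test".

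**The concern.** The declared endpoint and the named test do not concern the same measurement. An analyst who follows the Analysis line would compare connectivity between T1 and T2, and would have no stated method for the change in regional activation. Either result could then be presented as the Aim 2 finding.

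Section 7.1 gives variance estimates for sizing a larger study as a goal of a pilot. If only the named test is reported, the imaging estimate carried forward would describe connectivity, not the endpoint that the protocol calls primary.

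**Working it through.** No arithmetic applies. The two power calculations in Section 7.1 are not tied to imaging: one uses a hormone effect on binge eating, and the other is a generic detectable effect size. The check is to set the text side by side.

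1. **Which outcome is primary?** Section 3.2, Section 6 (Clinical Assessments), the opening of 7.2 and the Primary Outcomes text all say activation. Connectivity appears only in the Aim 2 methods and Analysis text. It is not listed as an endpoint in 3.2 or under Primary Outcomes.

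2. **Which T1–T2 tests are named?** There are three uses of a paired t test.
   - Aim 1: EPSI binge-eating score and weekly binge frequency.
   - Aim 2: seed-based connectivity.
   - Secondary outcomes: BIS/BAS, SPSRQ and the Kirby discounting measure.

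   None covers regional activation. The mixed-model fallback under Missingness depends on considerable missing data and names no outcome.

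3. **Could connectivity stand in for activation?** Not by the plan's own description. It defines functional connectivity as statistical dependence between activations in different regions. It says the gPPI interaction terms are there "to describe the unique effect of these interactions above and beyond the main effects of seed time courses and task conditions". An activation analysis estimates the task-condition main effect. The interaction terms describe what is left beyond it.

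4. **Does the dependent-variable line bridge the two?** No. It is labelled as percent signal change in the regions, which is an activation measure, but its sentence says that connectivity will be assessed. It merges two quantities under one entry.

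5. **Is an activation comparison specified elsewhere?**
   - The Study Summary says that scans before and at the end of treatment serve to examine changes in activation, and gives within-group comparison as the reference. No method is stated.
   - Section 2 promises within-subject change. No method is stated.
   - The image-processing text in Section 6 plans an event-related BOLD analysis within the regions. No T1–T2 comparison is stated.
   - Aim 2 pairs the three regions with T1 versus T2. The Analysis line that follows applies its test to connectivity.
   - The tertiary correlations use change in activation against change in binge eating. A correlation does not alter if the same constant is added to every participant's activation change, so it says nothing about the mean change.

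**Count:** four places name activation as a primary endpoint or outcome, and none names connectivity as one. One T1–T2 imaging test is named, on connectivity. None is named for activation in any of the three regions.

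**The case against.** The best reply is that the intent is plain. Aim 2 lists the three regions as dependent variables and T1 versus T2 as the independent variable. The Study Summary speaks of changes in activation, Section 6 plans the regional BOLD analysis, and the other T1–T2 comparisons in 7.2 use a paired t test. The gPPI model also contains the task-condition regressors, so task main effects are in the model. On this view one line is missing and another is muddled.

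Much of that stands. A reader might infer that the investigators meant to replace activation with connectivity, or that activation will not be compared at all. The documents support neither: the hypothesis, the variable listing and the tertiary correlations all point to a planned comparison of activation. What does not follow is that the method can be read off. The only sentence that names an imaging test attaches it to the other quantity, and no T1–T2 comparison of the task main effects is stated.

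Two further points are fair. No section commits to reporting an SD of change for any endpoint, so that omission is not peculiar to imaging. And enrolment was closed on 1/6/2022 (Protocol Updates), with the remaining participant(s) to finish before termination. The planned sample of 15 and the use of the estimates in a larger study are therefore less certain than Section 7.1 assumed.

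**Conclusion.** The point holds as a mismatch between the declared endpoint and the stated analysis. The named Aim 2 test, followed as written, does not analyse the primary imaging outcome, and no other text supplies a test or estimate for it. This rests on reading activation and gPPI connectivity as distinct, which the plan's own description requires.

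A reader might want to express the mismatch as a loss of power. The documents do not allow it. They give no figure linking a change in connectivity to a change in activation, and the former could be smaller, larger or of opposite sign. Connectivity is also to be evaluated with voxel-wise models, so a power figure for one single-value t test would not describe it.

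The stakes are limited, because this is a pilot that does not focus on significance and recruitment ended early. The point should still be fixed, because it concerns one of the two primary outcomes and is easy to correct.

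**What to change.** In Section 7.2, Aim 2:

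- State a paired T1–T2 comparison of mean percent signal change in each of the three regions, for one named contrast. Win versus non-win outcomes is a candidate, since both the image-processing text in Section 6 and Aim 2 name it.
- Report the mean change, SD of change and 95% CI for each region.
- List percent signal change and connectivity as separate dependent variables.
- Label the gPPI connectivity analysis separately. If connectivity is also meant to be primary, amend 3.2 and 7.2 to say so.

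The cost is plan wording and a minor extraction of regional values from scans already planned. No new data are needed.

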## 7.3 Subject Population(s) for Analysis

Studies consistently observe post-ovulation exacerbations of binge eating in both women with and without a clinical ED. Thus, our sample population of women with a binge-eating syndrome is empirically supported.

## 8 Ethical Considerations

This study is to be conducted according to US and international standards of Good Clinical Practice (FDA Title 21 part 312 and International Conference on Harmonization guidelines), applicable government regulations and Institutional research policies and procedures.

This protocol and any amendments will be submitted to a properly constituted independent Ethics Committee (EC) or Institutional Review Board (IRB), in agreement with local legal prescriptions, for formal approval of the study conduct. The decision of the EC/IRB concerning the conduct of the study will be made in writing to the investigator and a copy of this decision will be provided to the sponsor before commencement of this study. The investigator should provide a list of EC/IRB members and their affiliate to the sponsor.

All subjects for this study will be provided a consent form describing this study and providing sufficient information for subjects to make an informed decision about their participation in this study. See Attachment for a copy of the Subject Informed Consent Form. This consent form will be submitted with the protocol for review and approval by the EC/IRB for the study. The formal consent of a subject, using the EC/IRB-approved consent form, must be obtained before that subject undergoes any study procedure. The consent form must be signed by the subject or legally acceptable surrogate, and the investigator-designated research professional obtaining the consent.

# 9 Study Finances

## 9.1 Funding Source

This study is financed through a private foundation grant through the Foundation of Hope, Raleigh, NC.

## 9.2 Conflict of Interest

Any investigator who has a conflict of interest with this study (patent ownership, royalties, or financial gain greater than the minimum allowable by their institution, etc.) will have the conflict reviewed by a properly constituted Conflict of Interest Committee with a Committee-sanctioned conflict management plan that has been reviewed and approved by the study sponsor prior to participation in this study. All UNC investigators will follow the University conflict of interest policy.

## 9.3 Subject Stipends or Payments

Participants will be compensated up to \$200 upon completion of the study. Payment is processed through the UNC Department of Psychiatry. Only participants who complete all study activities as outlined below will receive the full \$200. This will be clearly outlined and stated in the informed consent. If a participant is withdrawn due to an adverse event, they will be provided prorated compensation.

Payment will be made in the below increments, with a majority occurring at T2. All potential participants will receive \$10 for completing the enrollment visit (T0), regardless of their final eligibility for the study.

	Total Amount	When Received
Enrollment Visit (T0)	\$10	Completion of T0
Screening Period and Ovulation Testing	\$10	Completion of T2
First fMRI Visit (T1)	\$70	Completion of T2*
Check-in Visits (x2): \$5.00 each	\$10	Completion of T2
Second fMRI Visit (T2)	\$70	Completion of T2*
Medication Adherence and Weekly Survey Completion \$0.90 per weekly survey (12 surveys); \$0.10 per day for medication compliance (84 days). Total: \$19.80, rounded to \$20 for 100% compliance	\$20	Completion of T2
Follow-up (T3)	\$10	Completion of T3

\*participants will receive a portion of T1/T2 incentive immediately at the T1/T2 visit as part of their participation in the MIDT. During the MIDT, participants can “win” money. Money won during the task is given to participants immediately, at the end of the study visit (this is what makes the task “rewarding”). This will be subtracted from their total incentive for participation, so that the total amount of money that can be received is \$200 for everyone.

## 10 Publication Plan

The results of this proposal will be published in the scientific literature and presented at relevant conferences. The trial will be registered with clinicaltrials.gov.

## 12 Appendices

# Appendix A. Study Procedures Flow Chart

**Figure 2**

## Appendix B. COVID Procedures

Due to the COVID-19 pandemic, this study as described above will be modified as described below. These procedures are only in response to the COVID-19 pandemic. If we are able to begin recruitment, enrollment, and study visits ‘as usual’ when it is safe, study procedures will resume as described.

**All remote portions of study visits will be conducted via WebEx calls. All scheduled WebEx visits will be password protected and only those with the password can enter the call.** WebEx has been approved by the UNC ITS as secure programs for PHI and sensitive information and the School of Medicine specifically recommends the use of WebEx for research study visits. WebEx is HIPAA compliant, ISO/IEC 27001:2013 certified, and approved for the transmission of PHI. Visits will be password protected and only those with the password can enter the study visit. Although Internet access is not a specific inclusion/exclusion criteria, because COVID19 requires converting many aspects of this study to virtual visits, we acknowledge participants will need to have access to the Internet.

